Inclusion and exclusion criteria: Men and women with T2D who are overweight and obese (BMI 25-50 kg/m2), 35-65 years of age, and sedentary (<60 minutes structured exercise/week) will be recruited from the local community and the University Hospital Cosmopolitan Diabetes Center. A cohort of non-obese (BMI 19-29kg/m2), recreationally active men and women aged 35-65 will be recruited to serve as healthy control subjects. Patients with T2D will be classified based on physician diagnosis. Exclusion criteria: 1) cardiovascular disease including myocardial infarction, heart failure, coronary artery disease, stroke; 2) renal or hepatic diseases; 3) active cancer; 4) autoimmune diseases; 5) immunosuppressant therapy; 6) excessive alcohol consumption (> 14 drinks/week for men; >7 drinks/week for women); 7) current tobacco use; 8) pregnancy; 9) foot ulcers; 10) diabetic neuropathy; 11) mobility limitations; 12) uncontrolled hypertension (≥180 systolic / 100 diastolic mmHg).

For the experimental studies utilizing an ingestible telemetry sensor to monitor the core temperature of subjects, the following exclusion criteria will also be applied: 13) swallowing or esophageal disorders, or impairment of the gag reflex for experimental studies using the telemetry sensor; 14) gastrointestinal tract diseases or disorders; 15) individuals scheduled for nuclear magnetic resonance (NMR)/magnetic resonance imaging (MRI) scanning while the telemetry sensor is in the body.

Sub-study: A separate cohort of men and women ages 18- 65 will be recruited from the local community. Same exclusion as that listed above will be applied.

Number of subjects to be enrolled and justification: We plan to enroll a total 120 subjects to test hypotheses A, B, and the sub-study described below. This number will allow for subject dropout and provide a sufficient sample size to establish the efficacy of the interventions.

Experimental Studies:

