Hypothesis A: Increased walking decreases vascular PKC activation and ET-1 expression, thus leading to an improvement in insulin-stimulated leg blood flow. To test this hypothesis, T2D subjects will be randomized to a control non-exercise group (n=20) or walking group (n=20). Subject randomization will be accomplished by computerized randomization software. The walking program will consist of 45 minutes of walking (at 60% of VO₂ peak) 5 days per week for 8 weeks. Exercise interventions of similar intensity and duration have produced beneficial vascular effects in humans. Three days per week of the exercise intervention will be supervised and conducted at the MU Physical Activity and Wellness (MUPAW) center, a core facility in our department. Subjects will have the option to perform the other two walking sessions per week on their own. Prior to initiating the walking program, subjects will undergo a standardized exercise stress test with assessment of ECG. The workload corresponding to 60% of heart rate reserve will then be identified. Our study physician, [name], oversees these tests and interprets the ECG following American College of Sports Medicine (ACSM) guidelines. These exercise interventions and protocols in patients with chronic disease are routine at MUPAW.

Prior to participating in the study, subjects will provide written informed consent, complete a medical health history questionnaire, and receive randomization into experimental groups (walking v. control). Subjects will then be provided with a FitBit pedometer to wear throughout the 8-week period to quantify steps taken. Subsequently, before and after the 8-week period, subjects will be scheduled to come to the University Hospital Clinical Research Center (CRC) for a single testing day (Experimental Visit). On the testing day, subjects will arrive at 7am after an overnight fast, having not taken medications, and not exercised for 24-48 hrs. The cohort of healthy control subjects (n=20) will participate in the experimental visit once, with no exercise intervention.

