
The length of this visit will be 8 hours.

Hypothesis B: Increased leg vascular shear stress using a non-exercise stimulus (i.e., lower body heating) recapitulates the beneficial vascular effects of increased walking, including a reduction in vascular PKC activation and ET-1 expression, as well as an improvement in insulin-stimulated leg blood flow.

To test this hypothesis, T2D subjects (n=20) will undergo lower body heating for 60 min per day for 7 days at MUPAW. Potential minor deviations from this timeline may occur dependent on subject and study personnel availability. Lower body heating will be accomplished via water bath immersion at a temperature of 40.5°C to target a core temperature of 38.5°C, using a commercially available temperature-controlled water bath. Importantly, this protocol has improved glucose control in patients with T2D (Hooper, 1999) and women with polycystic ovarian syndrome (Ely et al., 2019). Additionally, this heating protocol improved vascular outcomes (blood pressure, endothelial function, and arterial stiffness) in women with polycystic ovarian syndrome (Ely et al., 2019) and sedentary men and women (Brunt et al., 2016). Furthermore, a 20-year longitudinal study showed that whole-body heating (via regular Finnish sauna use) protects against fatal cardiovascular disease and events (Laukkanen et al., 2015). Notably, whole-body heat therapy has been demonstrated to be safe for vulnerable clinical populations, improving prognosis and vascular outcomes of patients with chronic heart failure (Kihara et al., 2009) and peripheral arterial disease (Akermann et al., 2019; Thomas et al., 2017). Hooper (1999) hypothesized that the reason warm-water immersion improved glucose control in T2D and hence can be an effective treatment for the disease is that heating increases blood flow to the muscle. While a large portion of the flow is directed to the skin for heat dissipation, there is firm evidence that muscle blood flow is also markedly increased with local heating. Therefore, assessing the efficacy of passive heating as a potential therapy to improve vascular health and insulin-stimulated leg blood flow in patients with T2D is highly warranted.

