Prior to participating in the study, subjects will provide written informed consent and complete a medical health history questionnaire. Upon eligibility, subjects will be provided with an accelerometer to wear on their hip for a total of 14 days (7-days before, and 7-days during the heating intervention)- to quantify levels of physical activity in free-living conditions. Additionally, subjects will be provided with a 3-day food recall diary during the weeks they receive the accelerometer and before the experimental visits. Subsequently, before and after the lower body heating intervention, subjects will be scheduled to come to MU-PAW for a single testing day (Experimental Visit). On testing days, subjects will arrive in the morning after an overnight fast, having not taken morning medications, and not exercised for at least 24hrs. The cohort of healthy control subjects (n=20) will participate in the experimental visit once. This cohort will also wear an accelerometer for 7 days to assess free-living physical activity. The healthy control cohort will not participate in the 7 day lower-body heating intervention.

On the Experimental Visit, body composition will be assessed with dual-energy X-ray absorptiometry. Subjects will then be placed supine in a quiet, climate-controlled room (22–23°C) and flow-mediated dilation in the brachial and superficial femoral arteries will be assessed as a marker of vascular function. Flow-mediated dilation will be measured using an ultrasound machine that images the arteries dilatory response to a blood

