We are interested in determining whether a single-bout of leg heating will result in favorable vascular adaptations, specifically enhanced vascular insulin sensitivity. To test this hypothesis, subjects (n=20) will be asked to participate in a single visit involving 1-hour of unilateral leg heating. The contralateral leg will serve as the internal control. Leg assignment will be randomized by flipping a coin. Leg heating will be accomplished via water bath immersion at a temperature of 40-42°C, using our custom-made temperature-controlled water bath. During leg heating, the subject is seated and water reaches the level below the knee. This water temperature is below the threshold for pain sensation and has been shown by us and others to produce robust increases in limb blood flow. Ultrasound measures of leg blood flow will be performed during heating to document the increase in leg blood flow. Next, the insulin clamp, coupled with measures of leg blood flow, will be performed following standard procedures at the University Hospital CRC. Subjects will be instrumented for measures of heart rate (using standard lead II ECG), arterial blood pressure (using automated sphygmomanometry and beat-to-beat via Finometer), and leg blood flow (using duplex Doppler ultrasound and

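### Do six groups of 20 use up all 120 places, so that the stated allowance for dropout cannot exist?

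*Protocol*

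**What the plan says.** The Protocol section on the number of subjects and its justification reads "We plan to enroll a total 120 subjects to test hypotheses A, B, and the sub-study described below", and then "This number will allow for subject dropout and provide a sufficient sample size to establish the efficacy of the interventions". It gives no calculation.

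The group sizes appear later in the Protocol:

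- Hypothesis A, randomised part: "T2D subjects will be randomized to a control non-exercise group (n=20) or walking group (n=20".
- Hypothesis A, healthy controls: "The cohort of healthy control subjects (n=20) will participate in the experimental visit once, with no exercise intervention".
- Hypothesis B, heating group: "T2D subjects (n=20) will undergo lower body heating for 60 min per day for 7 days at MUPAW".
- Hypothesis B, healthy controls: "The cohort of healthy control subjects (n=20) will participate in the experimental visit once".
- Sub-study: "subjects (n=20) will be asked to participate in a single visit involving 1-hour of unilateral leg heating". The eligibility section makes these different people from the rest: "A separate cohort of men and women ages 18- 65 will be recruited from the local community".

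The eligibility section describes the healthy controls in the singular, as one cohort. The Compensation section lists a $200 payment for healthy controls once under Hypothesis A and once under Hypothesis B.

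The SAP specifies two-tailed t tests or ANOVA with significance at P<0.05. It says nothing about sample size.

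**The concern.** A total said to leave room for dropout should exceed the sum of the group sizes. Here it equals that sum, so on a plain reading there is no room. The justification also calls the number sufficient to establish efficacy without an effect size, standard deviation, power or dropout rate behind it.

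Losses would matter most in Hypothesis A. Subjects are randomised before the baseline testing day, then face an 8-week period with a clamp and biopsy visit on either side. Withdrawals would therefore come out of the randomised arms. If 20 were the number needed at analysis, any loss would leave an arm short and the comparison less precise than intended.

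**Working it through.** **1. The plan's own total.** A control 20 + A walking 20 + A healthy 20 + B heating 20 + B healthy 20 + sub-study 20 = 120. This matches the stated total exactly, with 0 places left over. It counts the healthy controls of A and B as different people.

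**2. Shared healthy cohort.** If the same 20 volunteers serve both hypotheses, the sum is 60 + 20 + 20 = 100. That leaves 120 − 100 = 20 places, and 20/120 = 16.7%.

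**3. What an allowance would need if 20 means completers.** Enrolment per group is 20/(1 − d), rounded up. The Protocol gives no dropout rate, so d is an assumption.

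| Assumed d | Per group | Six groups, all inflated | Five groups, all inflated | Six groups, only the three multi-visit T2D groups inflated | Five groups, only those three inflated |
|---|---|---|---|---|---|
| 5% | 22 | 132 | 110 | 126 | 106 |
| 10% | 23 | 138 | 115 | 129 | 109 |
| 15% | 24 | 144 | 120 | 132 | 112 |
| 20% | 25 | 150 | 125 | 135 | 115 |

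With separate healthy cohorts, every entry exceeds 120. With a shared cohort, 120 covers 15% loss in every group, or 20% loss in the three T2D groups that must return after an intervention.

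**4. What happens if 20 means enrolled.** The allowance then sits inside each group, and 10% to 20% loss leaves 18 to 16. The evaluable target is below 20 and is not stated.

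**5. Size of the effect on precision.** Take a two-sample t test, two-sided 0.05. The 80% power is an assumption, as the documents name none. The normal approximation to the detectable standardised difference is (1.960 + 0.842) × √(2/n). At n = 20 this is 2.802 × 0.316 = 0.886. The noncentral-t values are:

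| Completers per arm | Detectable difference (SD) | Power if the true difference is 0.909 SD |
|---|---|---|
| 20 | 0.909 | 80% |
| 18 | 0.961 | 75.5% |
| 17 | 0.991 | 72.9% |
| 16 | 1.024 | 70.1% |

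For the before-and-after heating group, the detectable standardised change is 0.660 at n = 20 and 0.724 at n = 17.

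The SD here is that of the analysed outcome. If change scores are analysed, with equal variances before and after and correlation r, then SD of change = SD × √(2(1 − r)). So 0.909 SD of change is 0.909 × √1.4 = 1.08 baseline SD at r = 0.3, 0.909 at r = 0.5, and 0.909 × √0.6 = 0.70 at r = 0.7. Neither document gives r.

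**The case for a change.** The strongest case for a change is that separate healthy cohorts are the more natural reading. The Hypothesis A healthy visit is an 8-hour clamp visit at the Clinical Research Center. The Hypothesis B visit is a 4-hour glucose tolerance visit at MU-PAW, with 7 days of accelerometry. Payment is listed twice, and counting the cohorts separately is the only way to reach 120. On any reading the allowance cannot be verified from the text, and the claim of sufficiency has no calculation behind it.

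Most of this stands. The sum is exact, the separate reading is the likelier one, and the basis for sufficiency is missing under every reading.

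The step to a non-existent allowance does not stand. It needs 20 to mean completers, and the Protocol never says so. Hypothesis A speaks of randomising subjects to groups of 20, which fits an enrolled number at least as well. It also needs two sets of healthy volunteers. Different visits and two payments would equally suit one person attending both, and the singular wording in the eligibility section leaves that open. Nor can delivered precision fall short of what the text claims, because the text claims no figure.

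**Conclusion.** No change to the plan follows. The six groups of 20 do sum to 120, and if A and B recruit separate healthy controls, no allowance is visible above the group sizes. The allowance may still lie within each group if 20 is the enrolled number, or come from a shared healthy cohort (20 places, 16.7%). The documents do not settle which.

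What is missing is explanatory detail: what 20 counts, whether the healthy cohort is shared, the expected dropout, and the basis for calling the size sufficient. The plan states no power, precision or evaluable number for its design to miss. Supplying the detail would leave enrolment, groups, tests and results as they are.

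The consequence is modest. At an assumed 15% to 20% loss from arms of 20, the detectable difference in Hypothesis A moves from about 0.91 to 0.99–1.02 SD. This rests on a two-sample t test at two-sided 0.05, 80% power, and assumed loss rates. It does not show that the trial is underpowered, because no target effect is given. Anyone reporting the trial can give the numbers randomised and analysed in each group, with confidence intervals that show the precision actually reached.

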On the Experimental Visit, body composition will be assessed with dual-energy X-ray absorptiometry. Subjects will then be placed supine in a guiet, climate-controlled room (22–23°C) and flow-mediated dilation in the brachial and popliteal arteries will be assessed as a marker of vascular function. A pressure sensor (tonomter, the size of a pencil) will be placed over the skin of the neck region to obtain the pressure wave form in the carotid artery. Next, the insulin clamp, coupled with measures of leg blood flow, will be performed following standard procedures at the University Hospital CRC. Subjects will be instrumented for measures of heart rate (using standard lead II ECG), arterial blood pressure (using automated sphygmomanometry and beat-to-beat via Finometer), and leg blood flow (using duplex Doppler ultrasound and contrast-enhanced ultrasound, CEU). After a minimum of 20 min supine rest, baseline cardiovascular measurements will be collected, blood samples obtained and the hyperinsulinemic-euglycemic clamp will start. Briefly, insulin diluted in 0.9% saline with 5 ml of the subject's blood is infused with a 10 min priming dose followed by a constant infusion at 40 mU·m-2·min-1, a dose used to mimic postprandial insulin concentrations. Glucose is maintained at fasting values throughout via a variable 20% dextrose infusion. Leg blood flow, arterial blood pressure, and heart rate will be collected for 5-min periods at 20-min intervals throughout the 180-min clamp allowing the magnitude as well as the temporal profile of these variables to be determined. For microvascular blood flow using CEU, measurements will be performed before and during the first 60 min of insulin stimulation. Briefly, assessment of microvascular perfusion utilizing CEU involves ultrasound imaging of the leg skeletal muscle and abdomen during the administration of one vial (1.3mL) of an ultrasound contrast agent diluted in 30mL of 0.9% saline that will be given using a handheld syringe pump through the IV at a rate of 2mL/min. This agent, called Definity, is composed of tiny microbubbles smaller than the size of a red blood cell. These bubbles stay inside the blood vessels and go where the red blood cells go. This contrast agent allows us to evaluate microvascular blood flow. Definity has been FDA approved for use in humans during ultrasound of the heart cavity and has been shown to be safe. The total volume of blood drawn per insulin clamp will be less than 120mL. During the hyperinsulinemic-euglycemic clamp, [name] will perform the skeletal muscle biopsies from the vastus lateralis muscle, following established procedures at the CRC. Skeletal muscle biopsies will be processed for molecular characterization via immunofluorescence, PCR, and Western blotting. Assessments will include expression/activity of PKC, MAPK, eNOS, and ET-1, among other targets related to insulin signaling and vascular health.

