Date: 07/08/2020

Protocol Version Number: 10

Principal Investigator: [name]

Project IRB #: 2008181

Application Title: Restoring vasodilator actions of insulin in patients with type 2 diabetes (Role of physical activity in restoring vascular insulin sensitivity in skeletal muscle of patients with type 2 diabetes).

Collaborating Investigators:

[name]

[name]

Statistical Analysis Plan

All statistical analyses were completed with SPSS Statistics (version 23) or GraphPad Prism software (version 8.1.1 or 9.3.0). Statistical comparisons were performed by two-tailed t test or analysis of variance (ANOVA), as appropriate, followed by Tukey's or Bonferroni adjusted pairwise comparisons when significant interactions were found. For all statistical tests, significance was accepted at $P<0.05$.

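### Hypothesis A randomises before the baseline Experimental Visit, with no withheld allocation or masked assessment described, so baseline measures are open to influence from the arm

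*Protocol*

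**What the plan says.** The protocol, under Hypothesis A, sets out the steps in order. After consent and a health questionnaire, subjects "receive randomization into experimental groups (walking v. control). Subjects will then be provided with a FitBit pedometer". The testing visits follow: "Subsequently, before and after the 8-week period, subjects will be scheduled to come to the University Hospital Clinical Research Center". Randomisation is by computer software, 20 to control and 20 to walking. Nothing is said about when the arm is disclosed or who is kept unaware of it.

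All outcome baselines named for Hypothesis A come from that visit:
- "flow-mediated dilation in the brachial and popliteal arteries will be assessed as a marker of vascular function";
- "Leg blood flow, arterial blood pressure, and heart rate will be collected for 5-min periods at 20-min intervals throughout the 180-min clamp", with contrast-enhanced ultrasound before and during the first hour of insulin;
- biopsies, where the operator "will perform the skeletal muscle biopsies from the vastus lateralis muscle".

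Subjects arrive fasted, "having not taken medications, and not exercised for 24-48 hrs", and rest supine for at least 20 minutes before the clamp baseline. A stress test must precede the walking programme. The protocol does not say whether that test falls before or after the baseline visit.

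The nearest text to masking is the coding of data under Sources of materials and Protection against risk. Its purpose is confidentiality, and the investigators hold the codes. The SAP says only that "Statistical comparisons were performed by two-tailed t test or analysis of variance (ANOVA), as appropriate"; it mentions neither masking nor adjustment for baseline.

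**The concern.** The baseline visit is half of the pre-to-post contrast. If the arm is known by then, two different things can go wrong, and they should be kept apart.

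**(a) Early activity.** Subjects are sedentary by inclusion. One who learns of allocation to walking may become more active before the baseline visit. If walking improves the outcome, part of the benefit is then already present at baseline, the contrast is diluted and power falls. If walking has no effect, early walking cannot shift the baseline, so this route cannot produce a false positive.

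**(b) Arm-related acquisition, reading or other behaviour at baseline.** Ultrasound results depend on how images are obtained and read. Knowledge of the arm could move baseline values with no walking effect at all, and that raises the false-positive rate. A walking-arm baseline that is too low exaggerates benefit; one that is too high hides it.

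Subjects cannot be masked to walking, so the order of steps is the practical safeguard for the baseline measures.

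**Working it through.** **Order of steps.** Read in sequence, Hypothesis A gives: consent, questionnaire, randomisation, FitBit, baseline Experimental Visit, 8-week period, second Experimental Visit. Allocation therefore precedes every outcome baseline. Neither document mentions concealment, delayed disclosure, or masking of operators, laboratory readers or analysts. That the arm is actually known at the baseline visit is an inference from this order and this silence.

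**Size.** The plan gives no effect size, SD, correlation or power, so there is no figure of its own to reproduce. What follows is an illustration.

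Inputs:
- 20 per arm (protocol, Hypothesis A); two-sided 5% (SAP).
- Assumed: pre-post correlation ρ = 0.6 (range 0.5 to 0.7), and equal SD at both visits.
- Assumed: a shift s of 0.10 or 0.25 SD in one arm at baseline and none at week 8.

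Formulas (noncentral t, both tails summed):
- Unadjusted change: SE = √(2(1−ρ)) × √(2/20) = 0.894 × 0.316 = 0.283; bias = s; 38 df.
- Baseline-adjusted: SE = √(1−ρ²) × √(2/20) = 0.8 × 0.316 = 0.253; bias = ρs; 37 df.

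*Route (a), walking works, unadjusted.* The effect giving 80% power is 0.813 SD (0.813/0.283 = 2.87).
- s = 0.10: 0.813 − 0.10 = 0.713; 0.713/0.283 = 2.52; power 69%.
- s = 0.25: 0.813 − 0.25 = 0.563; 0.563/0.283 = 1.99; power 49%.

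Starting again from 80% power, the figures are 70% and 53% at ρ = 0.5 (effect 0.91 SD), and 67% and 44% at ρ = 0.7 (effect 0.70 SD).

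*Route (b), no walking effect.*

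| Shift | Unadjusted, ρ = 0.6 | Range, ρ 0.5–0.7 | Adjusted, ρ = 0.6 | Range, ρ 0.5–0.7 |
|---|---|---|---|---|
| 0.10 SD | 0.10/0.283 = 0.35; error 6.4% | 6.1–6.8% | 0.06/0.253 = 0.24; error 5.6% | 5.4–6.1% |
| 0.25 SD | 0.25/0.283 = 0.88; error 13.8% | 12.0–16.9% | 0.15/0.253 = 0.59; error 8.9% | 7.3–11.7% |

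Baseline adjustment reduces the bias but does not remove it.

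**Cancellation.** If the outcome is the response to insulin within a visit, a shift common to resting and stimulated flow would partly cancel. I give no figure for this, because it depends on the SD and correlation of the response itself, which the documents do not state.

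**The case against.** The strongest case against is that exposure is narrow and its effect unproven.

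- **The FitBit is not arm-specific.** All randomised subjects receive it, so reaction to wearing it is not tied to one arm by design. This stands.
- **The programme cannot start straight away.** The stress test must come first. This stands for the supervised programme, but it does not stop a subject becoming active unprompted.
- **The visit is standardised.** Fasting, no medications, no exercise for 24–48 hours and supine rest limit short-term influences. They do not cover longer-lasting behaviour change, or the acquisition and reading of flow-mediated dilation.
- **An operator unmasked at baseline is also unmasked at week 8.** This stands. Bias in the same direction at both visits would partly cancel in the change. Any bias at week 8 is untouched by reordering. The error rates under route (b) therefore describe only a shift confined to baseline.
- **It may be too late.** The SAP is written in the past tense, so most or all subjects may already be randomised. The reordering helps only those who are not.

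A reader might go further and infer that the baselines are biased, that no masking was used, or that the error rates above also apply to early walking. The documents support none of these. They show an order of steps and are silent on masking, which does not prove its absence. The error rates assume no walking effect, and early walking then cannot move the outcome.

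**Conclusion.** The point holds as a weakness of the stated sequence: allocation precedes the baseline outcome measures, and no safeguard is described. It is an opportunity for bias of unknown size and direction, and it concerns the randomised comparison in Hypothesis A only. On the assumed inputs, the effect on error is small at 0.10 SD and becomes material at shifts nearer 0.25 SD. The loss of power from early activity is about 11 points at 0.10 SD (80% to 69%) and 31 points at 0.25 SD (80% to 49%). Every shift and correlation used is an assumption. The change should be made because it costs almost nothing, not because harm has been shown. Confidence is medium.

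**What to change.** **Subjects not yet randomised.** In the protocol, Hypothesis A, state that the baseline Experimental Visit is completed first, and that the subject is then randomised or the arm disclosed. This removes any influence of allocation on baseline. It needs no new visit or procedure. The small downside is that training must be scheduled after that visit. A subject may still withdraw on learning the arm, which would then be a missing week-8 value.

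**Subjects already randomised.** Report the order actually used. Where coded ultrasound, immunofluorescence, PCR or blot files exist, have existing staff read them with arm and visit masked. The documents do not say which files are kept, so this is conditional. The cost is recoding the files and having someone who does not read them hold the key. It addresses reading bias at both visits; it cannot undo effects on behaviour or image acquisition.

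**Optional sensitivity check.** Compare week-8 values alone between arms. A shift confined to baseline cannot bias this comparison, but it remains exposed to unmasked acquisition at week 8. It uses existing data at some loss of precision: at ρ = 0.6 its SE is √(2/20) = 0.316, which is 12% larger than the unadjusted change contrast (0.316/0.283) and 25% larger than the baseline-adjusted one (0.316/0.253).

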Date: 07/08/2020

Protocol Version Number: 10

Principal Investigator: [name]

Project IRB #: 2008181

Application Title: Restoring vasodilator actions of insulin in patients with type 2 diabetes (Role of physical

activity in restoring vascular insulin sensitivity in skeletal muscle of patients with type 2 diabetes).

Collaborating Investigators:

[name] [name]

Study purpose: The purpose of the present project is to determine the effects of increased walking and shear stress on insulin-stimulated leg blood flow in sedentary patients with type 2 diabetes (T2D).

This study is classified as a clinical trial and is registered on Clinicaltrials.gov #NCT03203694.

Background: The notion that habitual aerobic exercise increases insulin-induced vasodilation is largely founded on rodent studies, hence the urgent need for human studies, especially in T2D. For example, it remains unknown if increased walking, the most common form of physical activity, enhances skeletal muscle vasodilator actions of insulin in T2D. In addition, the molecular mechanisms by which exercise improves vasoreactivity to insulin have not been examined in humans. We propose that in T2D patients who are sedentary (i.e., the vast majority), increased walking signifies a vital strategy to correct the impairment in insulin-stimulated leg blood flow. We hypothesize that this restoration of vascular actions of insulin is associated with a reduction of protein kinase C (PKC) activation and endothelin-1 (ET-1) expression in the vasculature of skeletal muscle. Indeed, we contend that increased physical activity and associated hemodynamic forces (e.g., shear stress) are a direct form of vascular medicine in humans. We capitalize on this concept by proposing that recapitulation of exercise-like hemodynamic signals (i.e., increased shear stress) using a non-exercise stimulus (i.e., lower body heating) will lead to favorable vascular adaptations, including enhanced vascular insulin sensitivity.

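### Hypothesis B heats one T2D group with no unheated T2D group repeating the visit, so it can estimate a before-after change but cannot establish the efficacy of 7-day heating or test whether heating matches walking

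*Protocol*

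**What the plan says.** **Aim.** Under Study purpose, the protocol sets out to "determine the effects of increased walking and shear stress on insulin-stimulated leg blood flow in sedentary patients with type 2 diabetes". The sample size paragraph (Number of subjects to be enrolled and justification) says that 120 subjects will "provide a sufficient sample size to establish the efficacy of the interventions".

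**Hypothesis B.** Lower body heating "recapitulates the beneficial vascular effects of increased walking, including a reduction in vascular PKC activation and ET-1 expression", and improves insulin-stimulated leg blood flow. To test this, 20 T2D subjects are heated for 60 minutes a day for 7 days and attend an Experimental Visit before and after. The outcomes, from the visit description and Figure 1, are leg blood flow during a 75 g OGTT, brachial and superficial femoral flow-mediated dilation (FMD), pulse wave velocity, and endothelial cells taken through an elbow-crease catheter. The only other group is a healthy cohort (n=20), which attends once and is not heated.

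**Hypothesis A.** T2D subjects are randomised to walking (n=20) or no exercise (n=20). Walking is "5 days per week for 8 weeks". The visits include an insulin clamp and a vastus lateralis biopsy, and "flow-mediated dilation in the brachial and popliteal arteries will be assessed as a marker of vascular function".

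**Sub-study.** Twenty subjects have one leg heated once; a coin flip assigns the leg and the other leg is the control.

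**SAP.** It offers two-tailed t tests or ANOVA, as appropriate, at P<0.05. It ties no test to any hypothesis.

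**The concern.** Two statements about heating need something the design does not contain.

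- **Efficacy.** To attribute a change to 7 days of heating, one needs to know how T2D subjects would have changed over the same week without it. No group supplies that. The healthy cohort is seen once, so it has no change score.
- **Matching walking.** To test whether heating reproduces walking's effects, one needs a planned comparison on common measures. None is planned, and most measures differ.

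As the plan stands, a significant paired t test in 20 heated subjects could be reported as proof of efficacy, or as heating doing what exercise does, and no planned analysis could contradict it.

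**Working it through.** **Step 1. Head count, the only figure the plan gives.** The stated groups are A walking 20, A control 20, A healthy 20, B heated 20, B healthy 20 and sub-study 20. These sum to 6 × 20 = 120, which matches the plan if the two healthy cohorts are separate. One shared cohort gives 100. No effect size, SD, power or dropout rate is stated, so no power calculation can be reproduced.

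**Step 2. Can Hypothesis A's control arm stand in?**

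| Feature | A, non-exercise arm | B, heated group |
|---|---|---|
| Allocation | randomised against walking | single group |
| Interval between visits | 8 weeks | 7 days of heating |
| Test site | University Hospital CRC | MU-PAW |
| Stimulus for leg flow | insulin clamp, fixed infusion rate | 75 g OGTT |
| Leg FMD artery | popliteal | superficial femoral |
| Tissue | vastus lateralis biopsy | arm-vein endothelial cells |

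Brachial FMD is shared, but over a different interval and at a different site. The arm does not supply the missing change for Hypothesis B.

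**Step 3. What n=20 paired can deliver.** The 95% CI half-width is t(0.975, n−1)/√n in SDs of the paired difference: 2.093/√20 = 0.47 SD. If 18 complete it is 0.50, and if 16 complete, 0.53. This interval covers sampling error only. Any drift unrelated to heating sits inside the estimate.

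**Step 4. What drift would do to the test.** The documents give no drift size, so these values are assumptions. Let d be a favourable drift in SDs of the paired difference, with zero heating effect. The test statistic is noncentral t with 19 df and noncentrality d√20, and the critical value is ±2.093. The SAP's test is two-tailed, so both tails count.

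| Assumed d | d√20 | Favourable tail | Other tail | Total rejection |
|---|---|---|---|---|
| 0.05 | 0.224 | 4.0% | 1.5% | 5.5% |
| 0.1 | 0.447 | 6.2% | 0.85% | 7.1% |
| 0.2 | 0.894 | 13.3% | 0.25% | 13.6% |
| 0.3 | 1.342 | 24.6% | 0.06% | 24.7% |

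The nominal rate is 5%. With one week between tests and activity monitored, the upper rows are the more plausible. The argument does not depend on any row: without an unheated T2D group, d cannot be estimated from the trial.

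**Step 5. What a control group would require.** Twenty more T2D subjects would bring the total to 120 + 20 = 140 with separate healthy cohorts, or 100 + 20 = 120 with a shared one, before dropout. The difference detectable with 80% power (two-sided 0.05) would be 0.91 SD of change for 20 v 20, against 0.66 SD for the paired test with n=20.

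**The case against.** **A hypothesis may be causal.** This is fair, and it limits the point. A reader might infer that the protocol asserts that heating works, because the Background says it "will lead to favorable vascular adaptations, including enhanced vascular insulin sensitivity". That clause is governed by a statement that the investigators are proposing it. The paragraph on importance of knowledge likewise asks *if* shear stress improves flow, and its term, leg heating, is close to the sub-study's wording, so it may not refer to Hypothesis B alone. The Hypothesis B section says that assessing efficacy is warranted, which is rationale. The clear overstatement of capability is in the sample size paragraph. The verb *recapitulates* is a hypothesis that the design cannot test.

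**Equivalence is not claimed.** Correct: no equivalence or non-inferiority test is stated, and the word could mean only the same direction of effect. But direction of effect also needs an unheated change to compare with.

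**Safeguards exist.** Accelerometry before and during heating, food diaries and fasting visits limit or describe drift. They do not estimate it. The sub-study has a sound concurrent control, but for one below-knee bout in a general 18–65 cohort.

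**Inferences the documents do not support.**
- That arm-vein cells are the wrong tissue for Hypothesis B. The phrase "endothelin-1 (ET-1) expression in the vasculature of skeletal muscle" describes the walking mechanism; Hypothesis B says only vascular PKC and ET-1.
- That small drift badly inflates error. At 0.05 to 0.1 SD the two-tailed rate is 5.5% to 7.1%.
- That regression to the mean is at work. Eligibility does not select on flow or FMD.

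**Conclusion.** The point holds as a limit on what may be concluded. Hypothesis B, as designed, estimates uncontrolled within-participant changes over 7 days of heating, with a 95% CI half-width of about 0.47 SD at n=20. It cannot establish the efficacy of 7-day heating, and it cannot test whether heating reproduces the effects of walking. On those two matters the plan is wrong as written.

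This rests on the design facts, which the documents state plainly. The rejection rates are illustrations under assumed drift and a zero heating effect, and the true drift may be small. Nothing here suggests that heating is ineffective or that the data lack value.

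**What to change.** 1. **Hypothesis B section.** State that the hypothesis is tested as a paired before-after change in the listed outcomes: leg blood flow during the OGTT, brachial and superficial femoral FMD, pulse wave velocity, and endothelial-cell measures. Report each with a 95% CI, label it uncontrolled, and do not rank the outcomes. Name this paired contrast in the SAP.
2. **Comparison with walking.** Do not treat *recapitulates* as a tested claim. Any comparison with Hypothesis A is descriptive.
3. **Efficacy wording.** In the sample size paragraph, limit the claim to establish efficacy to the randomised walking comparison. In the Hypothesis B section and the paragraph on importance of knowledge, state that the 7-day heating result is an uncontrolled change. Causal wording for heating is available only for the single-bout, leg-versus-leg sub-study.
4. **If the analyses are complete.** The SAP is written in the past tense. In that case, keep the hypothesis of protocol version 10 on record and apply these limits to the reported conclusions.

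**Cost.** A few sentences in the protocol and one in the SAP, and a weaker claim for heating. No participant, visit or sample is added.

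**Alternative, not recommended.** A concurrent unheated T2D group would be needed only if the causal claim is kept. With 20 subjects it would bring the total to 140 (120 if the healthy cohort is shared) before dropout, and it would not by itself permit a test against walking.
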